7. MDGA
8. Hematology and serum chemistries blood samples
9. Clinical Immunology Tests blood sample
10. Serum pregnancy test (women of childbearing potential)
11. Blood sample for biomarker analyses

12. Obtain skin biopsies
13. Dispense ixazomib 4 mg capsules for the 4-week cycle number 1 (3 capsules)
14. The first dose of ixazomib for cycle 1 will be taken on study Day 1 during the study visit and observed being taken by a member of the study team.
15. Instruct the participant on taking ixazomib day 8 and day 15 of the first cycle

18.3.2 Study Day 14 (Week 2) Lab Visit (+4 days)

1. Hematology and serum chemistries blood samples
2. Determine if ixazomib dose modification/interruption for hematologic or non-hematologic AE/SAE is indicated (Section 9.2 Ixazomib Dose Modification or Interruption); if so, patient is to be contacted by phone to:
 - A. Discontinue taking any remaining ixazomib.
 - B. Arrange for additional study office visit (Unscheduled Study Visit, Section 19.0) prior to anticipated ixazomib dosing on day 15, if applicable.
 - C. Initiate additional test monitoring per Sections 9.2.2 Hematologic Toxicity and 9.2.3.3 Hepatic Impairment as applicable.
3. At add-on study office visit:
 - A. If applicable, collect unused ixazomib intended for use day 15.
 - B. Implement designated ixazomib dose modification / interruption and monitoring of clinical laboratory assessments specified in Sections 9.2.2 and 9.2.3.3 as applicable.
 - C. If applicable and on ixazomib cycle day 15 only, dispense a single revised ixazomib dose and observe being taken by a member of the study team.

18.3.3 Study Day 28 (Week 4) Office Visit (± 4days)

On study day 28 the following assessments and procedures will be performed:

1. Directed medical history including review of AEs/SAEs and concomitant medications that have been taken since the preceding visit.
2. If participant is taking background MMF, confirm dose and timing of dosing.
3. UCLA SCTC GIT 2.0 questionnaire
4. Hematology and serum chemistries blood samples
5. Clinical Immunology Tests blood sample
6. Serum pregnancy test (women of childbearing potential)
7. Blood sample for biomarker analyses
8. Spirometry and DLCO
9. Determine if ixazomib dose modification/interruption for hematologic or non-hematologic AE/SAE is indicated (see 9.2 Ixazomib Dose Modification or Interruption); if so, implement designated dose modification/interruption with clinical laboratory assessments more frequently if indicated for the next treatment cycle.
10. Collect unused ixazomib
11. Dispense ixazomib dosing indicated for the 4-week cycle number 2 (3 capsules)
12. If not interrupted, the first dose of ixazomib (day 1) for the cycle 2 will be taken during the study day 28 visit and observed being taken by a member of the study

team.

- Instruct the participant on taking ixazomib day 8 and day 15 of the second cycle.

18.3.4 Study Day 42 (Week 6) Lab Visit (+4 days)

- Hematology and serum chemistries blood samples
- Determine if ixazomib dose modification/interruption for hematologic or non-hematologic AE/SAE is indicated (Section 9.2 Ixazomib Dose Modification or Interruption); if so, patient is to be contacted by phone to:
 - Discontinue taking any remaining ixazomib.
 - Arrange for additional study office visit (Unscheduled Study Visit, Section 19.0) prior to anticipated ixazomib dosing on day 15, if applicable.
 - Initiate additional test monitoring per Sections 9.2.2 Hematologic Toxicity and 9.2.3.3 Hepatic Impairment as applicable.
- At add-on study office visit:
 - If applicable, collect unused ixazomib intended for use day 15.
 - Implement designated ixazomib dose modification / interruption and monitoring of clinical laboratory assessments specified in Sections 9.2.2 and 9.2.3.3 as applicable.
 - If applicable and on ixazomib cycle day 15 only, dispense a single revised ixazomib dose and observe being taken by a member of the study team.

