18.3.5 Study Day 56 (Week 8) Office Visit (\pm 4 days)

On study day 56 the following assessments and procedures will be performed:

- Directed medical history including review of AEs/SAEs and concomitant medications that have been taken since the preceding visit.
- If participant is taking background MMF, confirm dose and timing of dosing.
- UCLA SCTC GIT 2.0 questionnaire
- Hematology and serum chemistries blood samples
- Clinical Immunology Tests blood sample
- Serum pregnancy test (women of childbearing potential)
- Blood sample for biomarker analyses
- Spirometry and DLCO
- Determine if ixazomib dose modification/interruption for hematologic or non-hematologic AE/SAE is indicated (see 9.2 Ixazomib Dose Modification or Interruption); if so, implement designated dose modification/interruption with clinical laboratory assessments more frequently if indicated for the next treatment cycle.
- Collect unused ixazomib
- Dispense ixazomib dosing indicated for the 4-week cycle number 3 (3 capsules)
- If not interrupted, the first dose of ixazomib (day 1) for the cycle 3 will be taken during the study day 56 visit and observed being taken by a member of the study team.
- Instruct the participant on taking ixazomib day 8 and day 15 of the third cycle.

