18.3.6 Study Day 70 (Week 10) Lab Visit (+4 days)

1. Hematology and serum chemistries blood samples
2. Determine if ixazomib dose modification/interruption for hematologic or non-hematologic AE/SAE is indicated (Section 9.2 Ixazomib Dose Modification or Interruption); if so, patient is to be contacted by phone to:
 - A. Discontinue taking any remaining ixazomib.
 - B. Arrange for additional study office visit (Unscheduled Study Visit, Section 19.0) prior to anticipated ixazomib dosing on day 15, if applicable.
 - C. Initiate additional test monitoring per Sections 9.2.2 Hematologic Toxicity and 9.2.3.3 Hepatic Impairment as applicable.
3. At add-on study office visit:
 - A. If applicable, collect unused ixazomib intended for use day 15.
 - B. Implement designated ixazomib dose modification / interruption and monitoring of clinical laboratory assessments specified in Sections 9.2.2 and 9.2.3.3 as applicable.
 - C. If applicable and on ixazomib cycle day 15 only, dispense a single revised ixazomib dose and observe being taken by a member of the study team.

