7. MDGA
8. Hematology and serum chemistries blood samples
9. Clinical Immunology Tests blood sample
10. Serum pregnancy test (women of childbearing potential)
11. Blood sample for biomarker analyses
12. Complete pulmonary function tests including lung volumes and DLCO % predicted
13. Determine if ixazomib dose modification/interruption for hematologic or non-hematologic AE/SAE is indicated (see 9.2 Ixazomib Dose Modification or Interruption); if so, implement designated dose modification/interruption with clinical laboratory assessments more frequently if indicated for the next

treatment cycle.

14. Collect unused ixazomib
15. Dispense ixazomib dosing indicated for the 4-week cycle number 4 (3 capsules)
16. If not interrupted, the first dose of ixazomib (day 1) for the cycle 4 will be taken during the study day 84 visit and observed being taken by a member of the study team.
17. Instruct the participant on taking ixazomib day 8 and day 15 of the fourthcycle.

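### In cycles 1-3 the mid-cycle lab is tied to the study day with a forward-only window, so on most permitted dates it comes too late to protect the day-15 dose

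*Combined protocol and SAP*

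**What the plan says.** Section 9.1 sets dosing on cycle days 1, 8 and 15. Cycle 1 starts on study day 1 (18.3.1). For cycle 2, section 18.3.3 states that "the first dose of ixazomib (day 1) for the cycle 2 will be taken during the study day 28 visit"; for cycle 3, section 18.3.5 states that "the first dose of ixazomib (day 1) for the cycle 3 will be taken during the study day 56 visit". Both visits may move four days either way.

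Sections 18.3.2, 18.3.4 and 18.3.6 place the mid-cycle labs on study days 14, 42 and 70, each with a window of plus four days only. If a dose change is indicated, the participant is phoned to stop any remaining ixazomib (2.A, lettered as in 18.3.2) and staff are to "Arrange for additional study office visit (Unscheduled Study Visit, Section 19.0) prior to anticipated ixazomib dosing on day 15, if applicable" (2.B), with extra monitoring under 2.C. At the added visit the unused day-15 capsule is collected where that applies (3.A), the section 9.2 modification or interruption and its monitoring are put in place (3.B), and a replacement may be supplied: "If applicable and on ixazomib cycle day 15 only, dispense a single revised ixazomib dose" (3.C).

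The participant keeps the day-15 capsule at home (9.5) and is told at the cycle-start visit how to take it (18.3.1, 18.3.3, 18.3.5). No supplied text says to wait for the lab result. Section 17.2.3 describes these labs more generally, as monitoring between office visits in the first three cycles.

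**The concern.** Steps 2.A, 2.B, 3.A and 3.C show that one purpose of these labs is to let the team intervene on the day-15 dose, the last of the cycle. That needs a blood draw, with a result, before the capsule is swallowed. The lab is counted from study day 1 and can only drift later; the dose is counted from a cycle start that can move either way. The two clocks are not tied together.

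The stake is patient safety. A participant whose neutrophils, platelets or liver tests have crossed a section 9.2 threshold could follow the schedule exactly and take a full day-15 dose before anyone sees the result. These are the only scheduled blood tests between cycle-start visits, and section 7.2 says the expected adverse effects appear mostly in the first months. Safety and tolerability is the primary objective (6.1), and section 5.0 notes that ixazomib has not been studied together with MMF, whose hematologic and liver effects overlap with its own.

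**Working it through.** The plan gives no figure to reproduce; the check is a count of calendar dates.

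**Inputs.** Doses on cycle days 1, 8 and 15 (9.1). Cycle starts on study day 1, day 28 ± 4 and day 56 ± 4 (18.3.1, 18.3.3, 18.3.5). Lab windows 14-18, 42-46 and 70-74 (18.3.2, 18.3.4, 18.3.6). Lab turnaround is not given, so the counts use the draw date alone.

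**Formula.** Day-15 dose = cycle start + 14. Lead = dose day − lab day. A positive lead means the draw precedes the dose, zero the same day, negative after it.

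**Nominal starts (1, 28, 56).** Doses fall on days 15, 42 and 70. On the exact nominal lab dates the lead is 15 − 14 = 1, 42 − 42 = 0 and 70 − 70 = 0 days. Over the full lab windows:

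| Cycle | Dose day | Lab days | Before | Same day | After |
|---|---|---|---|---|---|
| 1 | 15 | 14-18 | 1 | 1 | 3 |
| 2 | 42 | 42-46 | 0 | 1 | 4 |
| 3 | 70 | 70-74 | 0 | 1 | 4 |
| Total | | 15 days | 1 | 3 | 11 |

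**Strict 28-day cycles (starts 1, 29, 57).** Doses fall on days 15, 43 and 71. Each cycle gives 1/1/3, in total 3/3/9.

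**Full start window, cycle 2.** There are 9 starts (days 24-32) and 5 draw days, so 45 combinations. Starts on days 24-27 give 4 × 5 = 20 draws after the dose. Start 28 gives 0/1/4, start 29 1/1/3, start 30 2/1/2, start 31 3/1/1 and start 32 4/1/0. Total: 10 before, 5 same day, 30 after. Cycle 3 (starts 52-60, draws 70-74) is identical. The lead runs from −8 days (start 24, dose 38, draw 46) to +4 days.

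**Would reversing the window be enough?** With a window of −4 to 0 days, cycle 1 is cured (5 of 5 before the dose). Cycles 2 and 3 still give 30 before, 5 same day and 10 after, of 45 each. The study-day anchor contributes as well as the direction of the window.

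**Lab on cycle days 12-14, counted from the actual first dose.** The lead is 15 − 12 = 3, 15 − 13 = 2 or 15 − 14 = 1 day. All 9 × 3 = 27 combinations precede the dose.

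**Room for a hold.** From the day-15 dose to the next cycle's first dose is nominally 28 − 15 = 13, 56 − 42 = 14 and 84 − 70 = 14 days. At the tightest permitted visits it is 24 − 15 = 9, 52 − 46 = 6 and 80 − 74 = 6 days. The 72-hour missed-dose rule (9.1.1) would therefore still admit a 3-day hold (6 − 3), but leave only 3 days before the next dose.

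**The case against.** Several counter-arguments stand.

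- The steps on the day-15 dose are conditional, so when the dose has been taken they simply lapse. A reader might infer that the protocol contradicts itself; it does not.
- A late draw is not useless. It meets the monitoring purpose in 17.2.3, and step 3.B can still put a modification or interruption in place for the next cycle.
- On the named dates no lab falls after the dose. A reader might take 11 of 15 as the chance that a participant is dosed before testing. The documents say nothing about how visits will be spread over the windows, so that reading has no support.
- Same-day draws may work. The day-28 and day-56 visits list bloods, the dosing decision and the observed dose together, and 17.2.3 uses the institution's own laboratory. The schedule seems to assume quick results, and 3.C fits that case.
- Section 9.2.2.1 pauses dosing for a low count, which in practice means a known one. Taking a capsule before the result is seen should not be read as a breach of it.
- Other safeguards exist: cycle-start labs, extra tests and visits when indicated (17.2.3, 19.0), investigator discretion (9.2.1), and weekly tests after dose reductions for cytopenia or liver abnormality.
- Appendix A and the investigator's brochure are not in the supplied text, so a hold instruction there cannot be excluded.

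These points limit the severity. They do not restore the safeguard: extra tests depend on clinical indication, which a silent cytopenia may not give, and weekly testing begins only after detection.

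**Conclusion.** The concern holds as a scheduling weakness. The plan intends an early check that can stop or reduce the day-15 dose in cycles 1-3, but its windows permit more dates on which that check is too late than dates on which it is in time: 11 of 15 at nominal starts, 9 of 15 with strict 28-day cycles, and 30 of 45 in each of cycles 2 and 3 over the start window. What is lost is action on that one dose; monitoring and action for the next cycle remain.

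The counts need no turnaround assumption. Same-day draws, not counted as late, succeed only if the result arrives before the capsule is taken. No bias in the results is claimed, and nothing in the documents would support such a claim. This is a cheap patient-safety improvement of minor to moderate severity.

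**What to change.** **Main change.** In 7.1, 17.2.3, 18.3.2, 18.3.4 and 18.3.6, count the mid-cycle lab from that cycle's actual first dose, with a window that closes before cycle day 15. Cycle days 12-14 give 1-3 days of lead for every permitted start.

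**Back-up.** In 18.3.1, 18.3.3 and 18.3.5, tell participants in cycles 1-3 not to take the day-15 capsule until the team has reviewed the result. This needs two companions. Step 3.C allows a revised dose on cycle day 15 only, so it must be amended to let a briefly held dose be given at the revised level. The hold should also be capped, for example at 1-2 days, and the dose otherwise skipped, to preserve the rest interval: at the tightest 6-day gap, a 2-day hold leaves 4 days. The hold should not replace the main change. Under the present windows it could delay the dose by 0-3 days in cycle 1, 0-4 days in cycles 2 and 3 at nominal starts, and up to 8 days at the earliest start, before any turnaround.

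**Cost.** Amendment wording and a revised visit calendar; the number of visits and tests is unchanged. The window shrinks from 5 days to 3. If labs are drawn only on weekdays (an assumption), Monday to Friday starts leave 1, 1, 2, 3 and 3 usable days. The draw is slightly earlier, so a fall in counts after the third dose would first be seen at the next cycle-start visit. A short delay remains possible if turnaround exceeds the lead.

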18.3.5 Study Day 56 (Week 8) Office Visit (\pm 4 days)

On study day 56 the following assessments and procedures will be performed:

- Directed medical history including review of AEs/SAEs and concomitant medications that have been taken since the preceding visit.
- If participant is taking background MMF, confirm dose and timing of dosing.
- UCLA SCTC GIT 2.0 questionnaire
- Hematology and serum chemistries blood samples
- Clinical Immunology Tests blood sample
- Serum pregnancy test (women of childbearing potential)
- Blood sample for biomarker analyses
- Spirometry and DLCO
- Determine if ixazomib dose modification/interruption for hematologic or non-hematologic AE/SAE is indicated (see 9.2 Ixazomib Dose Modification or Interruption); if so, implement designated dose modification/interruption with clinical laboratory assessments more frequently if indicated for the next treatment cycle.
- Collect unused ixazomib
- Dispense ixazomib dosing indicated for the 4-week cycle number 3 (3 capsules)
- If not interrupted, the first dose of ixazomib (day 1) for the cycle 3 will be taken during the study day 56 visit and observed being taken by a member of the study team.
- Instruct the participant on taking ixazomib day 8 and day 15 of the third cycle.

18.3.6 Study Day 70 (Week 10) Lab Visit (+4 days)

1. Hematology and serum chemistries blood samples
2. Determine if ixazomib dose modification/interruption for hematologic or non-hematologic AE/SAE is indicated (Section 9.2 Ixazomib Dose Modification or Interruption); if so, patient is to be contacted by phone to:
 - A. Discontinue taking any remaining ixazomib.
 - B. Arrange for additional study office visit (Unscheduled Study Visit, Section 19.0) prior to anticipated ixazomib dosing on day 15, if applicable.
 - C. Initiate additional test monitoring per Sections 9.2.2 Hematologic Toxicity and 9.2.3.3 Hepatic Impairment as applicable.
3. At add-on study office visit:
 - A. If applicable, collect unused ixazomib intended for use day 15.
 - B. Implement designated ixazomib dose modification / interruption and monitoring of clinical laboratory assessments specified in Sections 9.2.2 and 9.2.3.3 as applicable.
 - C. If applicable and on ixazomib cycle day 15 only, dispense a single revised ixazomib dose and observe being taken by a member of the study team.

18.3.7 Study Day 84 (Week 12) Office Visit (\pm 4 days)

On study day 84 the following assessments and procedures will be performed:

1. Directed medical history including review of AEs/SAEs and concomitant medications that have been taken since the preceding visit.
2. Physical examination, including vital signs (blood pressure, heart rate, and respiratory rate) and body weight (in kilograms)
3. If participant is taking background MMF, confirm dose and timing of dosing.
4. mRSS
5. UCLA SCTC GIT 2.0 questionnaire
6. Disease-status scales:
 - a. Mahler TDI
 - b. SHAQ
 - c. PtGA
7. MDGA
8. Hematology and serum chemistries blood samples
9. Clinical Immunology Tests blood sample
10. Serum pregnancy test (women of childbearing potential)
11. Blood sample for biomarker analyses
12. Complete pulmonary function tests including lung volumes and DLCO % predicted
13. Determine if ixazomib dose modification/interruption for hematologic or non-hematologic AE/SAE is indicated (see 9.2 Ixazomib Dose Modification or Interruption); if so, implement designated dose modification/interruption with clinical laboratory assessments more frequently if indicated for the next

treatment cycle.

14. Collect unused ixazomib
15. Dispense ixazomib dosing indicated for the 4-week cycle number 4 (3 capsules)
16. If not interrupted, the first dose of ixazomib (day 1) for the cycle 4 will be taken during the study day 84 visit and observed being taken by a member of the study team.
17. Instruct the participant on taking ixazomib day 8 and day 15 of the fourthcycle.

18.3.8 Study Day 112 (Week 16) Office Visit (\pm 4days)

On study day 112 the following assessments and procedures will be performed:

1. Directed medical history including review of AEs/SAEs and concomitant medications that have been taken since the preceding visit.
2. If participant is taking background MMF, confirm dose and timing of dosing.
3. UCLA SCTC GIT 2.0 questionnaire
4. Hematology and serum chemistries blood samples
5. Clinical Immunology Tests blood sample
6. Serum pregnancy test (women of childbearing potential)
7. Blood sample for biomarker analyses
8. Spirometry and DLCO
9. Determine if ixazomib dose modification/interruption for hematologic or non-hematologic AE/SAE is indicated (see 9.2 Ixazomib Dose Modification or Interruption); if so, implement designated dose modification/interruption with clinical laboratory assessments more frequently if indicated for the next treatment cycle.
10. Collect unused ixazomib
11. Dispense ixazomib dosing indicated for the 4-week cycle number 5 (3 capsules)
12. If not interrupted, the first dose of ixazomib (day 1) for the cycle 5 will be taken during the study day 112 visit and observed being taken by a member of the study team.
13. Instruct the participant on taking ixazomib day 8 and day 15 of the fifth cycle.

18.3.9 Study Day 140 (Week 20) Office Visit (\pm 4 days)

On study day 140 the following assessments and procedures will be performed:

1. Directed medical history including review of AEs/SAEs and concomitant medications that have been taken since the preceding visit.
2. If participant is taking background MMF, confirm dose and timing of dosing.
3. UCLA SCTC GIT 2.0 questionnaire
4. Hematology and serum chemistries blood samples
5. Clinical Immunology Tests blood sample
6. Serum pregnancy test (women of childbearing potential)
7. Blood sample for biomarker analyses
8. Spirometry and DLCO
9. Determine if ixazomib dose modification/interruption for hematologic or non-

hematologic AE/SAE is indicated (see 9.2 Ixazomib Dose Modification or Interruption); if so, implement designated dose modification/interruption with clinical laboratory assessments more frequently if indicated for the next treatment cycle.

10. Collect unused ixazomib
11. Dispense ixazomib dosing indicated for the 4-week cycle number 6 (3 capsules)
12. If not interrupted, the first dose of ixazomib (day 1) for the cycle 6 will be taken during the study day 140 visit and observed being taken by a member of the study team.
13. Instruct the participant on taking ixazomib day 8 and day 15 of the sixth cycle.

18.3.10 Study Day 168 (Week 24) Office Visit (\pm 4 days)

On study day 168 the following assessments and procedures will be performed:

1. Directed medical history including review of AEs/SAEs and concomitant medications that have been taken since the preceding visit.
2. Physical examination, including vital signs (blood pressure, heart rate, and respiratory rate) and body weight (in kilograms)
3. If participant is taking background MMF, confirm dose and timing of dosing.
4. mRSS
5. UCLA SCTC GIT 2.0 questionnaire
6. Disease-status scales:
 - a. Mahler TDI
 - b. SHAQ
 - c. PTGA
7. MDGA
8. Hematology and serum chemistries blood samples
9. Clinical Immunology Tests blood sample
10. Serum pregnancy test (women of childbearing potential)
11. Blood sample for biomarker analyses
12. Complete pulmonary function tests including lung volumes and DLCO % predicted
13. HRCT chest scan
14. Obtain skin biopsies
15. Collect unused ixazomib

18.3.11 Study Post-Treatment Follow-up Day 196-203 (Week 28-29) Office Visit (28-35 days after last study visit day 168/week 24)

On study day 196-203 post-treatment follow-up visit, the following assessments and procedures will be performed:

1. Directed medical history including review of AEs/SAEs and concomitant medications that have been taken since the preceding visit.
2. Physical examination, including vital signs (blood pressure, heart rate, and respiratory rate) and body weight (in kilograms)
3. If participant is taking background MMF, confirm dose and timing of dosing.
4. Hematology and serum chemistries blood samples
5. Clinical Immunology Tests blood sample

6. Serum pregnancy test (women of childbearing potential)
7. Blood sample for biomarker analyses

